We will send the consent to the participant via DocuSign, providing a participant-specific code in advance of sending the document via DocuSign, that will be required when the participant accesses and signs the consent. The consent discussion may take place via phone or video conference (e.g. Zoom). Participants will be given adequate time to consider the research study and ask questions prior to signing the consent form. When ready to sign, the participant will enter their code, verifying that the person signing the consent is the person that we spoke with previously, and sign the consent within the DocuSign system. Once the participant has electronically signed, the study team member obtaining informed consent will be notified that the electronic form is ready for his or her signature. Once signing is completed by all parties, both the study team and the participant can download the signed consent as a PDF. The study team will also have access to the audit log and the Certificate of Completion. The study team will load the signed consent into Epic.

After the Informed Consent process is completed, the study team member will document the informed consent process and file the IRB consent document to the research record.

Procedures prior to in-person research activities during COVID-19:

Individuals will be screened for change in baseline respiratory or systemic symptoms potentially attributable to COVID-19 or recent COVID-19 exposures on both the day before (via phone) and the day of any in-person study activities. If we are unable to reach a participant via phone for COVID screening purposes the day before an in person study visit, the research staff will administer the baseline respiratory or systemic screening questions immediately upon arrival at the study visit. The study visit may be canceled and rescheduled if an individual screens positive.

Study visit 1 (day 1):

Medical History:

Inclusion and exclusion criteria will be reviewed. A detailed medical history will be obtained to record relevant comorbidities and concomitant medications (See **Appendix B - Schedule of study surveys/standardized instruments** and **Supplemental Study Documents – Medical history forms**). Vital signs (temperature, blood pressure, heart rate, respiratory rate and oxygen saturation), including height and weight will be recorded.

Patient reported outcome measures:

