A member from the research staff will contact the participant by phone the day after the vaccine was given to ask about any side effects from the vaccine. If the research staff is unable to get in touch with the participant via phone for this safety monitoring phone call, the research staff will make two additional attempts to contact the participant via phone (up to a total of three contact attempts).

Safety monitoring phone call (day 7 +/-2):

Virtual safety monitoring:

A member from the research staff will telephone the participant approximately one week after the vaccine was given to ask about any side effects from the vaccine.

If the research staff is unable to get in touch with the participant via phone for this safety monitoring phone call, the research staff will make two additional attempts to contact the participant via phone (up to a total of three contact attempts).

Study visit 2 (day 30 +/- 5 days):

Interval medical history review:

Details of any acute illness (including bronchiectasis exacerbations) that have occurred since the previous in person study visit will be recorded in a written survey

(See Appendix B - Schedule of study surveys/standardized instruments Supplemental Study Documents – Interval Medical History Form). Additionally, any interval changes in medical history, medications or other vaccine

administration will be recorded.

Symptom diary:

The participant-completed symptom diary during the first month post-vaccination will be handed over to the study team.

Research phlebotomy:

Approximately 75cc's of blood will be drawn from the participant, processed and stored for subsequent analysis (see Appendix A schedule of sample collection).

Safety monitoring:

The vaccination site will be examined for each participant to ensure proper healing and evaluated for any signs of adverse reactions. A digital photograph of the vaccination site will be taken for each participant, without any identifying information included in the photograph, and will be uploaded into each participant's file that is safely stored under Virtual SAFE Desktop.

Study visit 3 (day 90 +/- 14 days):

Interval medical history review:

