Statistical Plan: Demographic and clinical characteristics of each study group will be described. Descriptive statistics, including proportions means and standard deviations and medians and interguartile ranges will be used to summarize BCG-stimulated immune response and NTMinduced cytokine and NTM killing activity at each time point (0, 30 days and 90 days) for each study group. Log-transformations of markers will be performed if distributional assumptions indicate. The primary statistical procedures will utilize linear mixed models to evaluate the mean difference in each marker from time 0 to 30 days and from time 0 to 90 days. The model takes the following form: $E[Y_{ij}] = b_0 + b_1 time_j + b_2 group_i + b_3 group * time + a'z_i + \alpha_i$ where Y_{ij} is the marker of interest for subject i at time j, group denotes the CF/NCFB/control status, time is a numeric visit number, z_i can include a vector of potential confounders and α is a subject-specific random effect to account for within-person correlations of the outcome while assuming the outcomes follow a Gaussian distribution. The parameter b₃ is the parameter of interest here as it quantifies the effect of CF/NCFB status on changing markers from baseline. Importantly, this model specifically allows us to account for baseline differences between groups, if they do exist. Secondary analyses will leverage the full longitudinal data collection of each of the three time points utilizing the previously described methods.

Interim Analysis: An interim safety assessment will be conducted once 30 CF, 30 NCFB, and 30 healthy controls have been enrolled and have completed the intradermal BCG vaccination and the 30-day blood draw.

d. Early stopping rules.

If there are two or more of the same Grade 3 adverse events (severe or medically significant but not immediately life threatening; hospitalization or prolongation of hospitalization indicated; disabling; limiting self-care or ADLs), or a single Grade 4 adverse events (life threatening consequences; urgent intervention indicated), the study will be halted until the Data Safety Monitoring Board (DSMB) can meet to discuss the appropriate actions that should be taken.

8. Risks

a. Medical risks, listing all procedures, their major and minor risks and expected frequency.

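### With time coded as visit number, b3 is half the group difference in change from day 0 to day 90; reported unscaled, it would halve the day-90 estimate and its confidence interval

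*Combined protocol and SAP*

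**What the plan says.** In section 7c (Statistical Plan), the primary mixed models are meant to "evaluate the mean difference in each marker from time 0 to 30 days and from time 0 to 90 days". One model is written, with a group term, a time term, their product and a subject-specific random intercept. In it, "time is a numeric visit number". The product coefficient b3 "is the parameter of interest here as it quantifies the effect of CF/NCFB status on changing markers from baseline". No multiplier or contrast is given to turn b3 into a day-90 effect.

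The next step in the plan is that "Secondary analyses will leverage the full longitudinal data collection of each of the three time points". This suggests that the primary fits are pairwise (baseline with day 30, baseline with day 90), although the plan does not say so outright.

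Section 4a and Appendix A number the blood-draw visits 1, 2 and 3, at baseline, day 30 and day 90. The sample size paragraph of 7c expresses effects as a mean difference in slopes, calls 40% clinically meaningful, and gives no unit of time for the slope.

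**The concern.** The target is a change from baseline, but the named parameter is a change per unit of visit number. The two coincide when the visits compared are one unit apart (day 30) and differ when they are two units apart (day 90). A report that follows the text literally would describe b3 as the day-90 effect on change from baseline when it is half of that.

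This matters because the study is a pilot whose effect sizes are meant to inform a larger trial, and because section 4a asks how each group responds across the two post-vaccination time points. Two primary estimates on different scales cannot be set side by side to answer that. A group deficiency of the same size at both visits would give a day-90 coefficient half as large as the day-30 one.

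**Working it through.** **Inputs.** Visit codes 1, 2 and 3 (section 4a, Appendix A). From 7c: 60 enrolled per arm with 10% dropout, so 60 × 0.9 = 54; within-person correlation 0.1; significance level 0.05; power 80%. Assumed here: two-sided tests, complete data, equal variance at each visit, marker SD set to 1.

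**The plan's own figure.** The detectable range of about 11% (TNFα) to 65% (IL17) cannot be reproduced, because the marker SDs come from an outside study and are not given. In SD units:

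- SD of a change = √(2 × (1 − 0.1)) = 1.342
- Standard error (SE) of a group difference in change = 1.342 × √(2/54) = 0.258
- Detectable difference at 80% power = (1.960 + 0.842) × 0.258 = 0.723 SD

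On the b3 scale for visits 1 and 3, the detectable value is 0.723/2 = 0.362 SD with SE 0.258/2 = 0.129. Their ratio is the same, so power is 80% on either scale.

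**Algebra.** Let D30 and D90 be the group differences (CF or NCFB against controls) in change from baseline. With two visits at codes t1 and t2, b3 = D/(t2 − t1).

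- Visits 1 and 2: b3 = D30/1 = D30.
- Visits 1 and 3: b3 = D90/2.
- Visits 1, 2 and 3 in one complete-data random-intercept fit: each subject's slope on equally spaced codes is (y3 − y1)/2, so b3 is again D90/2.
- Baseline and day 90 recoded 0/1: b3 = D90.

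Numbering the visits 0, 1, 2 instead of 1, 2, 3 makes no difference, because only the spacing enters.

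**Check on one simulated data set** (54 per arm, correlation 0.1, true deficiency −0.40 SD at both post-vaccination visits):

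| Fit | b3 | 95% CI | p |
|---|---|---|---|
| Visits 1 and 3, coded 1/3 | −0.1601 | −0.4058 to 0.0855 | 0.2014 |
| Same data, coded 0/1 | −0.3202 | −0.8116 to 0.1711 | 0.2014 |
| Visits 1, 2, 3 in one fit | −0.1601 | −0.4142 to 0.0940 | 0.2168 |

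The first two rows differ by exactly a factor of two in the estimate and both limits, with the same p-value. The third has the same estimate as the first, with a slightly different interval because the residual variance is estimated from more data.

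**Side by side.** Over 60 such data sets, mean b3 was −0.418 at day 30 (visits 1 and 2) and −0.187 at day 90 (visits 1 and 3). Coded 0/1, the day-90 mean was −0.374. The departures from −0.40 and −0.20 are simulation noise; the factor of two is exact.

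**Size of the error if the raw interval is read as the interval for D90.** At an estimate of −0.40 SD, the interval for D90 is −0.40 ± 1.96 × 0.258 = −0.906 to 0.106. The raw b3 interval is −0.453 to 0.053. The raw interval covers the true D90 with probability Φ(D90/SE + 1.96) − Φ(D90/SE − 1.96). That is about 66% at D90 = −0.40 SD and about 20% at −0.72 SD, against a nominal 95%.

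**The case against.** The strongest reply is that the halving is conditional. The plan writes one model, does not state the codes used inside a 0-to-90 comparison, and labels its time points 0, 30 and 90 days. An analyst could recode a two-visit data set as 0/1, or multiply b3 by the number of visit steps, and neither is excluded. A reader might infer that the day-90 result will certainly come out at half the true difference. The documents do not support that: it happens only if visit-number codes are kept and b3 is reported unscaled.

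It can also be said that b3 per visit is a legitimate slope difference, in line with the sample size paragraph, so the plan lacks only a unit. That is partly right, since the unit is indeed missing. But the text also gives a coding rule and says that b3 measures change from baseline, and at day 90 those two statements do not agree. Avoiding the error requires a step that the plan does not state.

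Two other strong readings go too far.

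- **The 40% mark.** A reader might infer that a true 40% lower fold-rise would be reported as 22.5% lower (1 − √0.6), or that a 64% deficit (1 − 0.6²) would be needed to show 40%. Those figures require a log transformation, which the plan makes only conditional, then exponentiating the raw b3 and judging it against 40% as a fold-rise. The plan commits to neither of the last two steps. Read as a ratio to the control slope, 40% is unaffected, because the factor cancels.
- **Apparent recovery.** A reader might infer that a constant deficiency would pass for recovery by day 90. The plan also requires summaries of the BCG-stimulated and NTM markers by group at 0, 30 and 90 days, and a halved coefficient would be visibly at odds with them.

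**Conclusion.** The point holds in conditional form. The stated coding of time does not deliver the stated day-90 contrast. If the model is fitted with visit numbers and b3 is reported as written, the day-90 estimate and both confidence limits are half the difference in 0-to-90 change. The factor is exact in the two-visit fit. It is exact for the estimate in a complete-data three-visit random-intercept fit, and approximate there if day-90 data are missing. The day-30 two-visit estimate is correct, so the two primary results would be on different scales.

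Rescaling changes no test, p-value or power. What is at risk is the reported size of the day-90 effect, its interval, and its comparison with day 30 and with a 40% mark that has no stated unit. This is worth correcting before analysis, but it does not undermine the planned tests.

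**What to change.** In section 7c (Statistical Plan), replace the numeric visit number in the primary model with visit as a categorical factor, baseline as reference, and report the group-by-day-30 and group-by-day-90 contrasts for CF against controls and NCFB against controls. Equivalently, if two-visit fits are intended, say so and code time 0 before vaccination and 1 at the post-vaccination visit being compared. The categorical form works whether the primary analysis is one fit or two.

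In the sample size paragraph, state that the 40% difference refers to the change from baseline at each visit.

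The cost is a few sentences of text. No new data are needed, and no power is lost in the two-visit comparisons.

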Lower NTM rate in CF in countries with standard BCG vaccination. We conducted an independent assessment of country-specific BCG vaccination policies per the WHO and NTM infection rates in 2019 as reported in the European CF Society Patient Registry^{19,20}. Low rates of NTM infection are often observed in European countries that universally vaccinate for BCG, whereas higher rates are seen in countries that have ceased their standard BCG vaccination strategies, especially countries in which vaccination was suspended in the 1980s or 1990s. Similar low NTM rates are seen in CF patients in Brazil²¹. These findings support the hypothesis that BCG vaccination may protect against NTM infection in people with CF.

4. Study Procedures

a. Study design, including the sequence and timing of study procedures (distinguish research procedures from those that are part of routine care).

Study design: This is a prospective, single center, non-randomized open-label study.

Study population: We plan to recruit 60 participants with CF from the JH Adult Cystic Fibrosis Center, 60 participants with NCFB from the JH Center for NTM and Non-CF Bronchiectasis, and 60 healthy control participants, gender and aged-matched to the CF arm, from the Johns Hopkins Center for Immunization Research (CIR).

Study location: Study participants will be seen at the Johns Hopkins Center for Immunization Research located at [name].

Study procedures:

Recruitment:

Recruitment for this study will be conducted either in person or remotely. Participants with CF and NCFB who are current patients of the Johns Hopkins Adult Cystic Fibrosis Center or the Johns Hopkins Center for Nontuberculous Mycobacteria and Bronchiectasis or other Johns Hopkins Pulmonary or Infectious Disease subspecialty clinics will be evaluated for study participation and approached for recruitment if eligible. Recruitment of healthy controls will occur through the Johns Hopkins Center for Immunization Research. Healthy controls will be gender and age-matched to within +/-5 years to the CF arm.

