e. Justification of why participants will not receive routine care or will have current therapy stopped.

N/A. All CF and NCFB participants will continue to receive routine standard care for bronchiectasis without any interruptions.

f. Justification for inclusion of a placebo or non-treatment group.

All participants will receive the intradermal BCG vaccination. There is no placebo or nontreatment group in this study. Following the results of this study, a larger, blinded, placebocontrolled trial may be designed. g. Definition of treatment failure or participant removal criteria.

The goal of this study is not to achieve efficacy in prevention of infections, but rather to assess biomarkers of immune protection that are altered by BCG vaccination of vulnerable populations. Study samples will not be analyzed in real time.

Given these factors, we do not have specific criteria for participant removal. If there are unforeseen circumstances during which a participant will not be able to present for study visits 2 and 3 (research phlebotomy visits), these will be evaluated on a case by case basis by the PI.

h. Description of what happens to participants receiving therapy when study ends or if a participant's participation in the study ends prematurely.

This is a single vaccine design and there is no further booster vaccine planned. Participants will continue to receive standard of care for their medical conditions during and after study completion.

5. Inclusion/Exclusion Criteria

• Inclusion criteria (CF/NCFB arms):

- Confirmed diagnosis of either CF or NCFB
- Adult male and non pregnant females ages 18-65 (inclusive)
- \circ FEV1 \geq 40%
- Willingness to participate in the study after all aspects of the protocol have been explained and written informed consent obtained.
- o Available for the study duration, including all planned follow-up visits

• Inclusion criteria (healthy controls):

- Adult male and non pregnant females ages 18-65 (inclusive)
- Negative HIV enzyme-linked immunosorbent assay (ELISA), rapid antibody test and/or confirmatory test, if necessary, at screening
- Willingness to participate in the study after all aspects of the protocol have been explained and written informed obtained
- Available for the study duration, including all planned follow-up visits

• Exclusion criteria (all arms):

- Current or prior history of active or latent TB (per report, not formally tested) or NTM infection
- Prior BCG vaccination

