c. Justification and safety information if non-FDA approved drugs without an IND will be administered.

See above. We have received an IND exemption from the FDA for the use of BCG in this study (see Supplemental study documents).

7. Study Statistics

- a. Primary outcome variable.
 - BCG Ag-specific cytokine release
- b. Secondary outcome variables.
 - NTM cross protectivity
 - Development of lung infections among the CF/NCFB arms during the 6-month period
 - Markers of trained immunity
- c. Statistical plan including sample size justification and interim data analysis.

Sample Size Calculations: The primary hypothesis tests are based upon enrollment of 60 individuals within each study arm while assuming a conservative attrition and dropout rate of 10% in each study group. Due to the pilot nature of this project, participants that drop out of the study will not be replaced. Power calculations were based upon testing a mean difference in slopes between groups assuming a within-person correlation of observations of 0.1 and have assumed that baseline response will not differ between groups; preliminary data for standard deviation of markers was obtained from Abate et al. We will have 80% power to detect changes in the mean difference in slopes ranging from approximately 11% (TNF α) to 65% (IL17) for markers of BCG-stimulated immune response, NTM-induced cytokine, and NTM killing activity between the CF and control groups and between NCFB and control groups at each time point at a significance level of 0.05. Given the heterogenous responses in individuals, we consider a mean difference in slopes of 40%, indicative of an immune response deficiency, between groups to be a clinically meaningful difference.

For detecting differences in TI, we will have 80% power to detect mean differences ranging from approximately 10-70% of TI at each time point between groups at a significance level of 0.05 assuming the same conditions as above, with the exception that the time variable will be the pre/post-stimulus condition. We will repeat these analyses for each time point. We have based power calculations using Cohen's f^2 (multiple correlation/1- multiple correlation) due to the lack of available data in these populations to estimate mean differences.

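### Covariates enter the primary model only as time-constant main effects, so the group difference in change (b3) is not adjusted for age or sex, and matching does not cover NCFB versus control

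*Combined protocol and SAP*

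**What the plan says.** Section 7c (Statistical Plan) gives a linear mixed model with time, group, their product, a covariate term and a subject random effect. The relevant part is "b_3 group * time + a'z_i". The covariate vector has a subject index and no time index. It "can include a vector of potential confounders", but none is named. The plan singles out b3, the group-by-time coefficient, as its target, and adds: "Importantly, this model specifically allows us to account for baseline differences between groups, if they do exist".

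Section 4a (Recruitment) says: "Healthy controls will be gender and age-matched to within +/-5 years to the CF arm". No matching of controls to the NCFB arm is described, and the study is non-randomized. Every arm admits ages 18 to 65 (section 5).

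The sample size text in section 7c states power for comparisons "between the CF and control groups and between NCFB and control groups at each time point". It also fixes how a difference will be read: "we consider a mean difference in slopes of 40%, indicative of an immune response deficiency, between groups to be a clinically meaningful difference".

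**The concern.** A covariate that enters as a main effect adjusts the level of a marker. The question here is about change after vaccination. The plan's statement on baseline differences is correct for level, but a reader could take it, together with the covariate term, to mean that b3 is adjusted for age and sex. It is not, whichever baseline variables are chosen.

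This matters most for NCFB versus control, where neither the design nor the model ties the arms together on age or sex. The descriptive table of group characteristics would reveal an imbalance without correcting b3. An age or sex difference in vaccine response could then be reported as an immune deficiency of bronchiectasis and carried into the larger trial that this pilot is meant to inform.

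**Working it through.** **1. The plan's own figure.** Section 7c claims 80% power for slope differences of about 11% to 65%. The marker SDs behind this come from a cited study and are not in the documents, so the range can be neither reproduced nor refuted. The stated inputs (60 per arm less 10% = 54, within-person correlation 0.1, alpha 0.05 taken as two-sided) give a detectable difference in change of (1.960 + 0.842) × √[2(1 − 0.1)] × √(2/54) = 0.723 marker SD. The point below does not depend on this figure.

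**2. Algebra.** Take one person at baseline and one follow-up, coded 0 and 1. Under the written model the expected change is b1 + b3·group, because the covariate term is the same at both visits and subtracts out. Suppose the true change also depends on a covariate z with coefficient c. The written model then estimates b3 + c × (mean z in NCFB − mean z in controls), with or without z as a main effect. Only a z-by-time term removes the second part.

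**3. Numerical check, complete visits.** In simulated data with 54 per arm, b3 was 0.11701 without covariates and 0.11701 with age and sex main effects (two visits), and −0.22694 both ways (three visits). Adding age-by-time and sex-by-time moved it to 0.1742 and −0.0693.

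**4. Possible size.** The documents give no NCFB age or sex distribution and no age or sex effect on the response, so these inputs are assumptions. Bias = age gap (in SDs) × effect on change (marker SD per SD of age). Variance of change = 2(1 − 0.1) + effect², and SE = √(2 × variance/54). For the middle case: bias 1.0 × 0.2 = 0.20, SE = √(2 × 1.84/54) = 0.261, ratio 0.77. A noncentral t with 106 df gives the closed-form column. The simulations used 1,500 trials per scenario.

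| Gap, effect | Bias (SD) | False positives, closed form | Simulated, with or without age main effect | Simulated, with age × visit |
|---|---|---|---|---|
| 0.5, 0.1 | 0.05 | 5.4% | 5.4% | 4.3% |
| 1.0, 0.2 | 0.20 | 11.8% | 12.3% | 4.7% |
| 1.5, 0.3 | 0.45 | 39.2% | 41.5% | 4.3% |

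For sex, a 10 to 30 point difference in the share of women times a 0.2 to 0.6 SD sex difference in response gives a bias of 0.02 to 0.18 SD and a false-positive rate of 5.1% to 10.4%.

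**5. Dropout.** With 60 per arm and 10% random dropout, the three scenarios gave 5.1/11.1/41.1% without age, 5.1/11.2/41.3% with an age main effect, and 5.4/5.1/5.0% with age × visit. The main effect moved single estimates by 0.003 to 0.007 SD on average (at most 0.06). In the largest scenario the mean bias was −0.442 SD with and without it.

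**6. Against the 40% threshold.** This comparison also needs an assumption. If the mean change in controls is 1 marker SD, a bias of 0.05 to 0.45 SD is 5% to 45% of the control slope; if it is 2 SD, 2.5% to about 22%.

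**The case against.** The harm is conditional. It needs both an age or sex difference between NCFB and controls and an effect of that factor on post-vaccination change, and the documents show neither. The low case is indistinguishable from 5% in practice. The 39% needs both assumptions at their maximum; with only one there (gap 1.5 with effect 0.1, or gap 0.5 with effect 0.3) the rate is about 9%. The 18 to 65 age limit also bounds the gap. All of this stands, and the rates are illustrations only.

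The equation may also be shorthand: it writes a single b2 and b3 for a three-level group, and it leaves the covariates open. But that openness concerns which variables enter, not their form, and no covariate-by-time term appears anywhere in the document.

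The strongest practical objection is that adjustment costs power exactly when the age gap is large. This is true, and the cost is set out with the fix. It does not rescue the unadjusted contrast, which is least trustworthy in those same cases. Age and sex are also not the only candidates: comorbidities and concomitant medications are recorded at visit 1 and would remain unadjusted.

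Finally, this is a pilot on biomarkers. That limits the consequences, but the plan still reads a slope difference as an immune deficiency.

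**Conclusion.** The concern holds. That the written covariate term cannot adjust change is exact for complete visits and very nearly so with 10% dropout. That no matching covers NCFB versus control follows from section 4a. The size of any bias is unknown: it is zero if the arms are alike on age and sex or if neither affects the response, and it reaches several tenths of a marker SD under the larger assumptions. For CF versus control the matching addresses age and gender by design, so the gap there is minor. This should be fixed before the NCFB contrast is interpreted. Confidence is medium, because the defect in the model is certain and its effect is not.

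**What to change.** In section 7c, replace the open-ended covariate term with a closed list: age, sex, age × visit and sex × visit. Use it for NCFB versus control and, for consistency, for CF versus control. Report b3 with and without these terms, and name the adjusted estimate in advance as primary for NCFB versus control. State that matching does not cover that contrast. Show the overlap of ages between the NCFB and control arms, and say that with poor overlap the adjusted estimate depends on a linear age effect. Regressing change on baseline, group, age and sex, or also matching controls to the NCFB arm, would be alternatives.

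The change is SAP wording, and age and sex are already available. The cost is precision: the SE of the contrast is multiplied by √(1 + d²/4), where d is the age gap in SDs. With an assumed age SD of 12 years:

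| Age gap (years) | SE increase | Power where the plan has 80% |
|---|---|---|
| 5 | 2% | 78% |
| 10 | 8% | 73% |
| 15 | 18% | 66% |
| 20 | 30% | 58% |

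With an age SD of 8 years, simulation gave a larger loss: power of roughly 64% at a 10-year gap and 51% at 15. The plan should state this loss.

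On linearity, one check limited ages to 18-65 and let the response drop by 0.6 SD only above age 50. Over realised gaps of 4 to 17 years, the linear term cut the bias from between −0.04 and −0.34 SD to between +0.02 and −0.04 SD. That is one response shape, not a general assurance.

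### A random-intercept model fitted to all three visits understates the standard error of the group-by-time term if true change differs between people; two-visit primary contrasts are not harmed.

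*Combined protocol and SAP*

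**What the plan says.** Section 7c, Statistical Plan, gives a linear mixed model with group, numeric visit number, their interaction b3 (the parameter of interest), optional confounders and one additive term per person, a "subject-specific random effect to account for within-person correlations". It names no random slope, unstructured covariance, variance by visit or group, or robust standard error. A single residual variance is not written down; it is the default reading of that silence.

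The primary procedures concern change from day 0 to day 30 and from day 0 to day 90. Then: "Secondary analyses will leverage the full longitudinal data collection of each of the three time points", using the same methods. Group is a three-level variable, although power is stated for CF against controls and NCFB against controls. Log-transformation is allowed if distributions call for it.

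Section 7c, Sample Size Calculations, introduces its clinically meaningful difference with "Given the heterogenous responses in individuals". Power was computed "assuming a within-person correlation of observations of 0.1", one value for all pairs of observations.

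**The concern.** A random intercept lets people differ in level but not in true change. If responses vary between people, as the sample-size text expects, each person's slope carries extra variance that the model has no term for. With three visits, the fit averages that extra variance with the scatter around each person's own line, and reports a standard error for b3 that is too small. Tests of group differences in response are then too liberal.

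The plan places the three-visit analysis among the secondary ones. It does not, however, say plainly that each primary contrast is fitted on its two visits alone. If all visits enter one fit, the same fault reaches the primary test.

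A conditional issue sits beside this. If all three groups are in one model with one residual variance, each pairwise comparison uses variance from a group outside it.

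**Working it through.** **Inputs from section 7c.** "enrollment of 60 individuals within each study arm", "assuming a conservative attrition and dropout rate of 10% in each study group", so 60 × 0.9 = 54 per arm; testing "at a significance level of 0.05" (two-sided assumed, as sidedness is not stated); within-person correlation 0.1. Slope SDs and group SDs are not in the documents and are varied as assumptions.

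**The plan's own figure.** With correlation 0.1, the SD of a change is SD × √(2 × 0.9) = 1.342 SD. The detectable difference at 80% power is (1.960 + 0.842) × 1.342 × √(2/54) = 0.723 marker SD. The stated 11% and 65% would imply marker SDs of 11/0.723 = 15% and 65/0.723 = 90% of the reference mean. No marker SD or mean is given, so the stated range can be neither confirmed nor refuted.

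**Two visits.** The within-person information is one change per person. Its variance is 2σ² plus the variance of true change, and both parts enter the estimated residual variance, so the standard error is right. Simulation (8,000 trials per case, 54 per arm, no true difference) with slope SD 0, 0.5, 1 and 2 residual SDs gave type I error of 5.5%, 5.2%, 5.4% and 5.2% with two groups, and 5.2%, 5.0%, 5.1% and 4.9% with three. Doubling the post-vaccination residual SD gave 5.1%.

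**Three visits, linear time.** Code visits 0, 1, 2, so the sum of squares about the mean is 2, and set the residual variance to 1. Let s be the slope SD per visit step.

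- True variance of one person's slope: V = 1/2 + s².
- Expected within-person mean square under the planned model: M = (53 × 2V + 54) / 107.
- Model SE divided by true SE: R = √[(M/2)/V].
- Type I error: 2 × [1 − Φ(1.96 R)].

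For s = 0.5: V = 0.75, M = (53 × 1.5 + 54)/107 = 1.248, R = √(0.624/0.75) = 0.912, type I error 7.4%.

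| s (residual SDs) | R | Type I, formula | Type I, simulated |
|---|---|---|---|
| 0 | 1 | 5.0% | 4.6% |
| 0.25 | 0.972 | 5.7% | 6.0% |
| 0.5 | 0.912 | 7.4% | 7.5% |
| 1 | 0.815 | 11.0% | 10.5% |
| 2 | 0.743 | 14.6% | 14.8% |

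At s = 0.3 the formula gives V = 0.59, M = 1.089, R = 0.961 and about 6.0%. For scale, s = 0.5 per step means true change over both steps has an SD of 1 residual SD. In separate simulations of 4,000 trials, a test on person-level slopes stayed between 4.5% and 5.7%.

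Unequal variance by visit, without slope differences, had smaller and mixed effects: residual SDs of 1, 2, 2 gave 3.1%, and 1, 1.5, 2 gave 5.5%.

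**Three groups sharing one variance, two visits.** The SE ratio for a pair is √(mean of the three variances / mean of the pair's two variances). For control, CF and NCFB SDs of 1, 1, 2, CF against control gives √(2/1) = 1.41, and NCFB against control gives √(2/2.5) = 0.89.

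| SDs (control, CF, NCFB) | CF v control, type I (simulated) |
|---|---|
| 1, 1, 1.5 | 2.0% |
| 1, 1, 2 | 0.7% |
| 1, 2, 2 | 3.9% |
| 1, 2, 1 | 8.4% |
| 2, 1, 1 | 8.4% |
| 2, 2, 1 | 9.4% |

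For SDs of 1, 1, 1.5 and 1, 1, 2, power for CF against control falls from 80% to Φ(2.80 − 1.96 × 1.19) = 68% and Φ(2.80 − 1.96 × 1.41) = 51%. Type I error for NCFB against control is 6.7% and 8.0%. With separate two-group fits and equal numbers, SD ratios of 1.5 and 2 gave 5.1% and 5.8%.

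**The case against.** The strongest reply is that the primary contrasts compare two visits, where differences between people in response do no damage, and that the three-visit analysis is secondary in a self-described pilot. This stands, provided each primary contrast really is fitted on two visits. The plan should say so.

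A second reply is that the single planning correlation of 0.1, with constant variance, is exactly the structure a random intercept describes. If it held, the three-visit test would be sound (4.6% simulated at s = 0). But it is a power assumption, and the same paragraph expects responses to differ between individuals.

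Two stronger readings are tempting. A reader might infer that the plan expects variances to differ by group, so that the pooled model is already known to be wrong. The documents speak only of individuals. A mixed-cause NCFB group could be more variable, but that is conjecture. Log-transformation may reduce such differences, and pairwise fits with equal numbers nearly remove the effect. A reader might also infer that one patient comparison is too liberal and the other too conservative. That holds only for some variance patterns: with SDs of 1, 2, 2 both comparisons are conservative, and with 2, 1, 1 both are liberal. The power losses above also apply only to effects sitting at 80% power. For TNFα, with 11% detectable, a 40% difference would still be found.

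**Conclusion.** The concern holds for any linear fit over all three visits. There the planned standard error of b3 is about 9% to 18% too small (R of 0.91 to 0.82), and type I error is about 7.5% to 11%, for a slope SD of 0.5 to 1 residual SD. At 0.3 or below the effect is slight. This rests on 54 per arm, equally spaced numeric visits, a two-sided 5% test and assumed slope SDs.

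It does not hold for primary contrasts fitted on two visits, so the documents do not support saying that the primary tests are invalid because individuals differ. The pooled-variance issue is a conditional risk of unknown direction, not a demonstrated error. Overall this is a cheap improvement that protects the stated error rate, plus a needed clarification of what enters each fit.

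**What to change.** In section 7c, Statistical Plan:

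1. State that each primary contrast is fitted on its two visits. Alternatively, take both contrasts from one model with visit as a category and an unstructured covariance.
2. In the three-visit analysis, replace the lone random intercept with an unstructured covariance or a random slope, or use standard errors clustered on the person.
3. State whether the groups are fitted together or in pairs. Where all three are pooled, allow variance by group or use robust standard errors.

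The cost is wording and a few lines of code, with no change for participants. A 3 × 3 unstructured matrix has 6 parameters against 2 for the planned model, or 6 × 3 = 18 if estimated separately by group. Either is manageable with about 54 per arm. The robust standard error is the lighter choice if a marker's model does not converge.
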